3.2 Study Objectives

To evaluate the Aortix System, specifically to assess:

- Safety:
 - Observe the nature, severity, and frequency of adverse events associated with the delivery, use, and retrieval of the Aortix Pump.
- Performance:
 - Successfully deliver the Aortix Pump to the descending thoracic aorta using the Aortix Delivery System;
 - Aortix Pump shall function as programmed for the duration of therapy;
 - Manage the Aortix Pump Power Lead and access site over the course of therapy without significant complications;
 - Successfully retrieve and remove the Aortix Pump using the Aortix Retrieval System.
- Effectiveness:
 - Evaluate hemodynamic decongestion (CVP, PCWP) during Aortix therapy;
 - Evaluate the effect of the Aortix therapy on kidney function;
 - Evaluate the impact of the Aortix Pump on clinical biomarkers of congestion.

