3.4.1 Inclusion Criteria

The patient must meet **ALL** of the following criteria:

- 1) Admitted to the hospital with a primary diagnosis of acute decompensated heart failure, either heart failure with reduced or preserved ejection fraction (HFrEF, HFpEF or HFmEF);
- 2) Worsening renal function (serum creatinine increase by ≥ 0.3 mg/dl [≥ 27 μ mol/L]) despite 48 hours of intravenous diuretic therapy. Increase can be compared to a baseline value taken within 90 days of hospitalization or during hospitalization;
- 3) Objective measure of congestion (Elevated PCWP [≥ 20 mmHg] OR Elevated CVP [≥ 12 mmHg]) obtained via catheter measurement;^{vii}
- 4) Persistent clinical signs and/or symptoms of congestion despite diuretic therapy (one or more of the following):
 - a) dyspnea at rest or with minimal exertion,
 - b) paroxysmal nocturnal dyspnea,
 - c) orthopnea,
 - d) lower extremity edema ($\geq 2+$),
 - e) elevated jugular venous pressure,
 - f) pulmonary rales,
 - g) enlarged liver or ascites,
 - h) pulmonary vascular congestion on chest x-ray;
- 5) Age >21 years and able to provide written informed consent.

^{vii} This assessment requires patient to sign informed consent.

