4.4 Day of Implant

4.4.1 Pre-Implant

Prior to Aortix Pump placement, placement of a pulmonary artery (PA) catheter is required to confirm hemodynamic congestion inclusion criteria. In addition, patients should have a pulse oximeter for periodic oxygen

saturation (SaO₂) measurements. The following serial PA catheter measurements will be performed throughout the study per **Appendix A**:

- Central Venous Pressure (CVP)
- Pulmonary Artery (PA) Pressure Systolic
- Pulmonary Artery (PA) Pressure Diastolic
- Pulmonary Artery (PA) Pressure Mean
- Pulmonary Capillary Wedge Pressure (PCWP)
- SvO₂ (As measured on mixed venous gas from PA catheter)

On the day of the implant procedure, prior to the deployment of the Aortix device, the following assessments should be made (note: any baseline tests that were done on the day of implant do not need to be repeated and it is acceptable to enter the same data into the respective CRF):

- Cardiovascular exam (edema, pulmonary auscultation, weight)
- Vital Signs (HR, BP, RR)
- Dyspnea evaluation
- Fluid Ins and Outs
- Hemodynamics to include the following:
 - CVP
 - PA systolic
 - PA diastolic
 - PA mean
 - PCWP
 - SvO₂ as measured by the PA catheter
 - SaO₂ as measured by the pulse oximeter
- Blood and urine labs should be collected as per **Appendix A**.

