4.8 Follow-Up

Patients with the pump implanted will be followed for adverse events for 30 days (± 7 days) post device retrieval. If implanted patients are still hospitalized at 30 days due to an adverse event relating to the device or any study related procedures, they must be followed until resolution of the adverse event, resolution with sequelae, or until a terminal event. Protocol required data collection for patients with the pump implanted will be for 30 days post device retrieval (± 7 days) per **Appendix A**.

The following data will be collected:

- NYHA classification
- Cardiovascular exam (edema, pulmonary auscultation, weight),
- Vital signs (HR, BP, RR)
- Dyspnea evaluation
- KCCQ, EQ5D
- Document current cardiovascular/renal medications and adverse events
- Blood and urine labs per **Appendix A**

Patients that have an attempted implant but do not have the pump implanted will be followed for adverse events for 30 days (± 7 days) post attempted implant. If attempted implant patients are still hospitalized at 30 days due to an adverse event relating to the device or any study related procedures, they must be followed until resolution of the adverse event, resolution with sequelae, or until a terminal event.

Terminal events are death, LVAD implantation, heart and/or kidney transplantation, dialysis, ultrafiltration or CRRT.

Patients who are enrolled and undergo anatomy screening and/or invasive hemodynamic measurements who do not have an attempted implant will be followed for adverse events for 7 days (\pm 2 days) post anatomic screening or invasive hemodynamics (whichever is later) or until hospital discharge, whichever is first.

Every attempt should be made to perform follow-up visits in person. Should extenuating circumstances (e.g., COVID-19 global pandemic travel restrictions) impact a site's ability to perform follow-up visits in person, notify the sponsor and make every attempt to collect the protocol required data via other means (e.g., telephone, video conference, blood and urine labs at a non-hospital lab).

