Appendix A: Schedule of Visits and Procedures

Category	Pre-Therapy		Aortix Therapy								Post-Therapy			
	Pre-Implant Period (Baseline Monitoring)	Day of Implant (Pre-implant)	Implant to Pump Retrieval					Once Congestion Target is Met and Within 12 hours of Beginning Weaning ^α	Day of Pump Retrieval (Pre-Pump Retrieval)	Cath-Lab Pre-Pump Retrieval	Post-Pump Retrieval Monitoring		Follow-Up: 30 days (± 7 days) from Pump retrieval	
	Current hospitalization once	once	Once (after pump deployed)	2 hours post implant ⊕ (± 30 min)	6 hours post implant (± 30 min) and Every 6 hours (± 1 hour) for 24 hours post implant	Every 24 h (± 2 hours)◆	Pump Speed Changes #	once	once	once	Every 24 h (± 2 hours)	Once at 72 hours post retrieval (± 4 hours) or discharge (whichever is earlier)	once	
Informed Consent ¹	X													
Med History	X													
NYHA Class	X											X	X	
Cardiovascular exam (edema, pulm auscultation, weight)	X	X				X		X				X	X	
Vital Signs: HR, BP, RR #	X	X		X	X	X	X	X		X		X	X	
Height	X													
Fluid Ins and Outs*		X*		X	X	X	X	X		X	X ^β			
Dyspnea Evaluation		X				X		X				X	X	
KCCQ, EQ5D	X												X	
HEMODYNAMICS														
CVP, PAP #		X		X	X	X	X	X		X				
PCWP #		X		X		X	X	X		X				
SvO ₂ , SaO ₂ **		X		X	X	X		X		X				
IMAGING														
Anatomy Screening	X													
Echo	X							X						
Fluoro Image			X							X				
MEDICATIONS	X		Record all cardiovascular/renal medications and medication changes.****										X	
OTHER EVENTS***			Record all adverse events, readmissions and mortality.											

1 Patient must sign informed consent before undergoing PA catheter placement for verification of inclusion criteria for objective measure of congestion or before undergoing imaging to assess anatomy for exclusion criteria for contraindicated anatomy.

α One time assessments to be taken once congestion targets are met or therapy has been deemed ineffective (decision has been made to retrieve device). These assessments should be performed before the pump speed is turned down; within 12 hours of beginning weaning.

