	Current hospitalization once	once	2 hours post implant (± 30 min)	Every 12h (± 1 hour)	Every 24 h (± 2 hours)	once	once	Every 24 h (± 2 hours)	Once at 72 hours post retrieval (± 4 hours) or discharge (whichever is earlier)	once
White Blood Cells, Platelets		X		X		X			X	X
Hemoglobin, Hematocrit		X		X		X	X	X	X	X
Sodium, Potassium, CO ₂ , Chloride	X	X		X		X			X	X
Bilirubin (total)	X	X		X		X			X	X
ALP, ALT/SGPT, AST/SGOT	X	X		X		X			X	X
Serum BUN or Urea	X	X		X		X			X	X
Serum Creatinine	X	X		X		X	X	X	X	X
eGFR	X	X		X		X	X	X	X	X
Plasma Free Hb (pfH)*		X			X	X	X	X	X	
LDH *		X		X		X	X	X	X	
aPTT + INR	X	X		X		X			X	
NT-pro-BNP or BNP**		X		X		X	X	X	X	X
Urine sodium (NA ⁺)		X	X	X		X			X	X
Urine creatinine		X	X	X		X			X	X
Urine urea		X	X	X		X			X	X
Urine osmolality		X	X	X		X			X	X
Urine Blood (Hemoglobin)*♦		X		X		X			X	
Urine albumin		X	X	X		X			X	X

*these values will be monitored if the pump speed is adjusted before weaning begins (see protocol section 4.5.2)

**clinical site may report either NT-pro-BNP or BNP for a patient, but should be consistent with all measurements for that patient during the study (do not mix NT-pro-BNP and BNP measurements for a given patient during the study). BNP is the preferred measurement.

⌚ 2 hours from time pump turned on during the deployment procedure.

◆ only required if collected per institution's standard of care urinalysis

α One time assessments to be taken once congestion targets are met or therapy has been deemed ineffective (decision has been made to retrieve device). These assessments should be performed before the pump speed is turned down; within 12 hours of beginning weaning.

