4 DEFINITION

Baseline, if not specified differently, will be defined as the last non-missing measurement collected during Pre-Implant Period (Baseline Monitoring). For parameters that are not collected during the corresponding time period, the baseline will be defined as the last non-missing measurement prior to Aortix Pump implantation procedure.

TEAEs will be defined as AEs not present prior to the start of study procedures, or AEs present before study treatment that worsened after the implantation procedure. If a partially missing date or time of onset allows the possibility that an AE may be a TEAE it will be assumed that it is a TEAE.

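### For creatinine, eGFR, BUN, four other lab rows and vital signs, the SAP takes baseline from Baseline Monitoring even when a Day of Implant value exists, so the descriptive changes include any pre-pump drift

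*SAP*

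**What the plan says.** SAP section 4 gives a default and a fallback. By default, baseline "will be defined as the last non-missing measurement collected during Pre-Implant Period (Baseline Monitoring"). For a parameter with no measurement scheduled in that period, "the baseline will be defined as the last non-missing measurement prior to Aortix Pump implantation procedure".

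Protocol Appendix A treats Baseline Monitoring and Day of Implant (Pre-implant) as two separate pre-therapy columns. The first is timed only as "Current hospitalization once". The row "Vital Signs: HR, BP, RR" is marked in both columns, and so are seven lab rows. Protocol 4.4.1 adds that "any baseline tests that were done on the day of implant do not need to be repeated", and allows the same result to be entered for both visits.

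SAP 7.9.2 (labs) and 7.9.3 (vital signs) summarise change from baseline descriptively and do not redefine baseline. Both list Day of Implant as a reported timepoint; only 7.9.3 also lists Baseline Monitoring. The creatinine and BUN boxplots in 7.9.2 show baseline, Congestion Target Met and Follow-Up. The patient-level plots of those two analytes start at implant.

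Other sections use a later reference. SAP 7.8.3 compares CVP, PCWP and natriuretic peptides from Day of Implant, and 7.9.8 gives dyspnea its own baseline, the last evaluation before the procedure.

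**The concern.** The study is single-arm, and one of its effectiveness objectives is to "Evaluate the effect of the Aortix therapy on kidney function". With no control group, each patient's own pre-pump value is the only comparator for creatinine and eGFR. A reader will naturally take the tabulated change as the change since the pump was started. If the reference value was taken earlier in the admission, that change also contains whatever happened between enrollment and implant. Protocol 4.3 asks that diuretics and inotropes be left unadjusted for 12 hours before placement unless medically necessary, in order to characterise the device's effect. A Baseline Monitoring value can predate that window.

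There is also an inconsistency within one display. Some rows of the blood-lab table would measure change from Baseline Monitoring and others from Day of Implant.

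**Working it through.** The plan states no figure for this point, so there is none to reproduce. The check is a count from the schedule and an identity.

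**1. Which parameters are affected.** Pre-therapy marks in the Blood and Urine Labs table of Protocol Appendix A:

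| Rows | Baseline Monitoring | Day of Implant | Baseline under SAP 4 |
|---|---|---|---|
| Electrolytes; bilirubin; ALP/ALT/AST; BUN or urea; creatinine; eGFR; aPTT + INR (7 blood rows) | yes | yes | Baseline Monitoring |
| WBC/platelets; Hb/Hct; plasma free Hb; LDH; BNP or NT-pro-BNP (5 blood rows) | no | yes | last value before implantation |
| Urine sodium, creatinine, urea, osmolality, hemoglobin, albumin (6 urine rows) | no | yes | last value before implantation |

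Total: 7 + 5 + 6 = 18 rows, of which 7 + 5 = 12 are blood. Seven of 18 lab rows are affected, and the blood-lab table mixes two baselines, 7 rows against 5. These are schedule rows, not table cells: the seven rows hold 4 + 1 + 3 + 1 + 1 + 1 + 2 = 13 analytes. Heart rate, blood pressure and respiratory rate are also marked in both columns.

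**2. What the change contains.** Write BM for the Baseline Monitoring value, DOI for the Day of Implant value and L for a later value. Then

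L − BM = (DOI − BM) + (L − DOI).

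The first term is pre-pump drift. It is zero when one result is entered for both visits. Otherwise it enters every later change for that patient, including the 72-hour/discharge and Follow-Up changes. Those two timepoints fall after retrieval, so they are not on-device changes under any baseline.

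**3. Size.** The documents give no drift. If a share p of patients have same-day baseline tests and the rest drift by a mean of d, the mean change shifts by (1 − p) × d. With assumed inputs, for creatinine and with either sign:

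| d (mg/dL, assumed) | p = 0 | p = 0.50 | p = 0.75 |
|---|---|---|---|
| 0.05 | 0.05 | 0.025 | 0.0125 |
| 0.10 | 0.10 | 0.05 | 0.025 |
| 0.20 | 0.20 | 0.10 | 0.05 |

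This shows how the shift scales. It does not estimate the shift in this trial.

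**4. What the planned tables let a reader recover.** The Day of Implant row reports mean(DOI − BM). Subtracting it from mean(L − BM) gives mean(L − DOI), provided that the same patients contribute to both. The spread cannot be recovered this way:

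Var(L − DOI) = Var(L − BM) + Var(DOI − BM) − 2 Cov(L − BM, DOI − BM),

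and the covariance is not tabulated. Nor do the median, minimum and maximum of L − DOI follow from the tabulated values, although SAP 3.2 plans these statistics for continuous variables. The boxplots have no Day of Implant box, and the patient-level creatinine and BUN plots omit the value that the tables use as reference.

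**5. The later end of the change.** SAP 7.14 says that Once Congestion Target Met is not collected in the latest CRF and substitutes the last pre-retrieval timepoint, but for urine output only. SAP 7.9.2 and 7.9.3 still tabulate Congestion Target Met. The on-therapy end of the change is therefore unsettled as well.

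**The case against.** The strongest reply is that the SAP follows the protocol's own vocabulary. Protocol 4.3 collects baseline blood labs under Baseline Monitoring, and Protocol section 7 plans summaries compared to baseline. Where the protocol wants a pre-implant reference it says so, as it does for the hemodynamic and natriuretic-peptide endpoints. Change from an enrollment baseline is a legitimate descriptive quantity, and the SAP never labels it an on-device effect. Day of Implant is a reported timepoint, so mean drift is visible. All values are listed, and the protocol says that each patient's data will be reviewed individually. Creatinine and eGFR are other data in a pilot of up to 30 implanted patients, with no test planned on them.

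Most of this stands, and it is why the severity is low. It does not explain why one blood-lab table should use two references, or why creatinine should have an earlier reference than BNP or dyspnea when kidney function is an objective.

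Three stronger readings are tempting, and the documents support none of them:

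- **The renal results will favour the device.** Nothing in the documents gives the direction of the drift.
- **The entry criterion proves drift.** "Worsening renal function (serum creatinine increase by" at least 0.3 mg/dL refers to a value from within 90 days of hospitalization or during it. It means that stability cannot be assumed; it says nothing about the interval from Baseline Monitoring to implant.
- **The primary endpoints are compromised, or data are lost.** CVP, PCWP and natriuretic peptides are compared from Day of Implant, urine output has its own rule in SAP 7.8.3.1, and the listings keep every value.

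**Conclusion.** The point holds as a low-severity weakness in the descriptive renal, laboratory and vital-sign summaries. For 7 of 18 lab rows and the three vital signs, the planned changes combine pre-pump drift with change after implant. The creatinine and BUN boxplots do the same, and the blood-lab table mixes two baselines. The amount cannot be determined from the documents: it depends on how many patients have same-day tests and on how far the others move before implant, and neither is stated. Mean drift can be read from the Day of Implant row. What the planned outputs lack is the SD, median and range of change from Day of Implant, and a boxplot that starts from it.

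This rests on reading SAP section 4 literally, with Baseline Monitoring meaning the Appendix A column of that name. SAP 7.9.3 supports that reading, because it lists Baseline Monitoring and Day of Implant as separate timepoints.

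**What to change.** - **SAP section 4.** Make the existing fallback the general rule: unless a section states its own rule (7.4.1 to 7.4.3 for medication windows, 7.8.3.1 for fluid intake and urine output), "the baseline will be defined as the last non-missing measurement prior to Aortix Pump implantation procedure". In practice this is the Day of Implant pre-implant value if available, otherwise the Baseline Monitoring value.
- **Limits of the rule.** Exclude labs drawn during the procedure. aPTT/INR is one of the seven rows, and Protocol Appendix B has heparin given once the sheath is in, so such a sample is not a pre-procedure value. Keep pre-implant hemodynamics taken in the cath lab eligible, since Protocol 4.2 allows the catheter to be placed there.
- **Displays.** Use this baseline in the 7.9.2 and 7.9.3 change tables and in the creatinine and BUN boxplots. Add Baseline Monitoring as a descriptive row in 7.9.2; 7.9.3 already has it.
- **On-therapy timepoint.** Reconcile 7.14 with 7.9.2 and 7.9.3, and state which timepoint the on-therapy change is taken to.

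The cost is a reworded definition with its two limits, one added row, a re-derived baseline flag and a clarification of the timepoint. No new data are needed, and parameters collected at only one of the two visits keep their present baseline.

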5 STUDY ENDPOINTS

5.1 Primary Safety Endpoints

- Rate of Occurrence of Serious Adverse Events (rate will be calculated and reported) [timeframe: enrollment to 30 day visit];
- Rate of Occurrence of Serious Procedure Related Adverse Events (rate will be calculated and reported) [timeframe: procedure to 30 day visit].

5.2 Device Performance Endpoints

- Deployment and retrieval procedures success rates (rates will be calculated and reported);
- Rate of occurrence of ADS, ARS and pump device-related adverse events (includes device malfunctions) (rate will be calculated and reported) [timeframe: implant attempt/implant to 30 day visit].

5.3 Primary Effectiveness Endpoints

- Clinically significant decongestion as measured by the PA catheter. Decrease in CVP or PCWP of > 20%. [timeframe: pre-implant vs when congestion target is met or therapy deemed ineffective];
- Change in Urine Output Assessed as the hourly rate of urine output before pump implanted vs hourly rate of urine output over the Aortix therapy period until congestion target met or therapy deemed ineffective;
- Decrease in BNP or NT-pro-BNP by 20% (pre-implant vs when congestion target is met or therapy deemed ineffective).

5.4 Additional Data to be Reported

- Rate of occurrence of all adverse events;
- Utilization of continuous renal replacement therapy (CRRT), ultrafiltration and dialysis;
- Change in serum creatinine;

- Change in eGFR;
- Change in diuretic doses;
- Change in urine sodium excretion;
- QoL changes from KCCQ and EQ5D;
- Change in dyspnea assessment;
- Changes in echo parameters (includes CO);
- Changes in cardiac output and cardiac power output;
- Rates of hemolysis as measured by Lactate Dehydrogenase (LDH), Plasma Free Hb (pfH) and urine hemoglobin.

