After signing informed consent, a urinary collection device will be placed, if not already present. A Foley catheter is recommended, but an external urine collection device may be used per institution requirements. The urine collection device will be placed (do not measure the urine collected during catheter placement) at least twelve (12 hours) before the Aortix Pump placement. If a urinary collection device is already in place, urine should be discarded. Output and intake should be strictly observed starting twelve hours prior to the scheduled implant. The urine collection device and the strict ins/outs monitoring will continue until the Aortix pump is retrieved. The first measurement of intake and output should occur at least six hours prior to Aortix placement and should be recorded every two hours until the pump is turned on. Measurements will occur at the frequency outlined in **Appendix A**.

Fluid ins should be monitored (IV and Oral) for the entire duration the urine collection device is in place with final measurements taken at the time of device retrieval.

Patients will receive standard medical therapy throughout the study. Patients should be on optimized medical therapy prior to being considered for Aortix Pump placement. To characterize the effect of the experimental device, physicians should not adjust the diuretic or inotrope dosing regimen during the twelve (12) hours prior to or the twelve (12) hours after Aortix Pump placement, unless medically necessary. **Diuretics and inotropes should not be adjusted for twelve (12) hours after the Aortix pump is turned on, however, after that point, while the Aortix pump is running, cessation of medications or down titration of diuretics, inotropes or other medications are allowed.** Adjustments of medical therapy can otherwise be made at any point during the study period at the discretion of the treating physician. All medications and medications adjustments will be captured on eCRFs.

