7.8.3.1 Fluid Intake / Urine Output

Cumulative Fluid Intake / Urine Output (mL) will be analyzed starting from the baseline measurement until Aortix retrieval. At each post-implant timepoint cumulative Fluid Intake / Urine Output (mL) will be defined as the total sum across all timepoints until corresponding post-implant timepoint. Cumulative Net Loss (mL) will be defined as the difference between Urine Output and Fluid Intake. Cumulative Fluid Intake, Urine Output and Net Loss will be presented graphically measurement from the baseline until Aortix retrieval by patient for As-Treated and PSC populations.

Hourly rate (mL/h) of Fluid Intake / Urine Output / Net Loss during Aortix therapy will be defined as cumulative Fluid Intake, Urine Output and Net Loss from baseline till the last pre-retrieval timepoint available divided by the number of hours (h) from baseline timepoint measurement till the last pre-retrieval timepoint available.

Baseline hourly rate (mL/h) of Fluid Intake / Urine Output / Net Loss will be defined as of Fluid Intake / Urine Output / Net Loss ([Urine Output] - [Fluid Intake]) from the last pre-baseline measurement to baseline divided by the number of hours (h) from the corresponding last pre-baseline timepoint till baseline.

Hourly rate of Fluid Intake / Urine Output / Net Loss at Baseline, during Aortix therapy and corresponding change from Baseline will summarized with descriptive statistics for As-Treated population.

Boxplots of Hourly rate of Fluid Intake / Urine Output / Net Loss will be provided by subgroup and overall to compare hourly rate during Baseline with hourly rate during Aortix therapy for As-Treated population.

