7.9.2 Laboratory assessments

Laboratory measurements will be listed and summarized for actual values and change from baseline with descriptive statistics for As-Treated and PSC populations by Timepoint (Day of Implant, Congestion Target Met, Post 72Hrs or Discharge and Follow-Up). Laboratory measurements will be separated into two categories – Blood Labs and Urine Labs.

Additional summary for lactate dehydrogenase (LDH), plasma free Hb (pfH) and urine hemoglobin will be provided for the As-Treated and PSC populations by Timepoint (Day of Implant, Congestion Target Met, Post 72Hrs or Discharge and Follow-Up).

In addition to the collected laboratory measurements, the following derived parameters will be listed and summarized as the part of Urine Labs category (with the Date/Time of measurement and Timepoint as for corresponding Albumin and Creatinine evaluations):

$$\text{UACR (mg/g)} = \frac{\text{Urine Albumin (mg/dL)}}{\text{Urine Creatinine (g/dL)}}.$$

Laboratory measurements (except for Blood Labs evaluations of Blood Urea Nitrogen and Creatinine) collected from the time of implant until Post 72Hrs or Discharge will be presented graphically by patient for As-Treated and PSC populations.

Blood Labs measurements of Blood Urea Nitrogen and Creatinine collected from the time of implant until Follow-Up will be presented graphically by patient for As-Treated and PSC populations.

Boxplots of Blood Urea Nitrogen and Creatinine will be provided by subgroup and overall to compare baseline results with Congestion Target Met and Follow-Up for As-Treated population.

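### Change in urine sodium excretion is a listed outcome, but the SAP only summarises the urine sodium laboratory value and never computes excretion

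*SAP*

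**What the plan says.** Protocol 3.3.4 and SAP 5.4 use the same words for the outcome: "Change in urine sodium excretion". Neither defines it.

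Protocol Appendix A (Blood and Urine Labs) schedules urine sodium on the day of implant before the procedure, 2 hours after the pump starts, every 12 hours, at the congestion-target assessment, at 72 hours or discharge, and at 30 days. It specifies no timed sodium collection.

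On analysis, SAP 7.9.2 says: "Laboratory measurements will be listed and summarized for actual values and change from baseline". The timepoints are "Day of Implant, Congestion Target Met, Post 72Hrs or Discharge and Follow-Up". It then says that "the following derived parameters will be listed and summarized as the part of Urine Labs category", and one formula follows, the albumin-creatinine ratio.

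Urine volume is measured separately. Protocol 4.3 says: "The urine collection device and the strict ins/outs monitoring will continue until the Aortix pump is retrieved". SAP 7.8.3.1 summarises "Hourly rate of Fluid Intake / Urine Output / Net Loss at Baseline, during Aortix therapy", with the change between them. Sodium does not appear in that section.

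The output list in SAP Appendix 1 has tables of urine labs and a listing of urine chemistry, but names no sodium excretion output. SAP 7.14 declares one departure from the protocol, the end timepoint for urine output.

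**The concern.** The outcome names one quantity and the analysis delivers another. A programmer who follows the SAP will tabulate change in the urine sodium laboratory value, and that row is the only thing a reader could take as the result for sodium excretion.

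The gap matters in this study because the device is intended to raise urine output, and urine output is a primary effectiveness endpoint. When flow changes, concentration is a poor guide to the amount excreted. A flat or falling concentration could accompany a real gain in sodium removal, and the reported row could then point the wrong way on a measure of decongestion.

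The SAP does give formulas for its other derived quantities: furosemide equivalents (7.4.2), hourly urine output (7.8.3.1), and cardiac output and cardiac power output (7.9.5.1). Sodium excretion has none.

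**Working it through.** The plan states no figure for urine sodium, so there is nothing to reproduce. The check has three parts.

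**1. Is excretion computed anywhere?** SAP 7.9.2 derives only the albumin-creatinine ratio, 7.8.3.1 derives volumes only, Appendix 1 names no excretion output, and 7.14 is silent. It is not computed.

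**2. Could the planned summary mislead?** Excretion rate (mmol/h) = urine sodium (mmol/L) × urine flow (L/h). Let r be the ratio of on-therapy to pre-implant concentration and f the same ratio for flow. The excretion ratio is r × f. For f above 1, concentration falls while excretion rises whenever 1/f < r < 1, that is, for any fall in concentration smaller than 1 - 1/f.

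| Flow ratio f (assumed) | Fall in concentration below which excretion still rises |
|---|---|
| 1.25 | 20% |
| 1.5 | 33.3% |
| 2 | 50% |
| 10 | 90% |

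Two of these ratios appear in the protocol: urine output rose by 100% in the ovine model (1.1; f = 2), and 10-fold on average in four first-in-human patients (1.2; f = 10).

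An illustration, with an **assumed** pre-implant value of 80 mmol/L at 100 mL/h, or 80 × 0.100 = 8.0 mmol/h:

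| On-therapy concentration | f | Excretion rate | Change in excretion |
|---|---|---|---|
| 56 mmol/L (-30%) | 1.5 | 56 × 0.150 = 8.4 mmol/h | +5% |
| 56 mmol/L (-30%) | 2 | 56 × 0.200 = 11.2 mmol/h | +40% |
| 48 mmol/L (-40%) | 1.5 | 48 × 0.150 = 7.2 mmol/h | -10% |
| 48 mmol/L (-40%) | 2 | 48 × 0.200 = 9.6 mmol/h | +20% |

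The percentages depend only on r and f, not on the assumed starting values. The third row shows that reversal is not automatic: there both quantities fall.

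**3. Can excretion be derived from what is collected?** This sets the two schedules side by side (Protocol 4.3, 4.5.1, 4.7 and Appendix A).

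| Period | Urine sodium | Urine volume | Excretion rate |
|---|---|---|---|
| Pre-implant | once, day of implant | every 2 h, from at least 6 h before | yes, once the interval is named |
| First 24 h | 2, 12, 24 h | 2, 6, 12, 18, 24 h | yes, by summing volumes between samples |
| After 24 h on therapy | every 12 h | every 24 h, plus speed changes, congestion target and pre-retrieval | yes, with a pairing rule |
| 72 h or discharge | once | only if the collection device is still in place | generally no |
| 30 days | once | none scheduled | no |

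The last two rows are two of the four timepoints in the SAP 7.9.2 summary.

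**The case against.** The best case for leaving the plan alone is this. Neither document defines excretion, so the item might be read loosely as urine sodium, and a relabel would remove the mismatch. Urine output is not hidden: it is derived, plotted by patient and listed, and so are the urine labs. Protocol section 7 says each patient's data will be reviewed individually, so a careful reader could see both for the same patient. The item is additional data in an uncontrolled study whose sample size was not statistically derived.

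Much of this stands, and it keeps the priority low. It does not close the gap. Seeing two series is not the same as reporting their product, and the item as worded promises the product. Relabelling is an acceptable alternative, but it is itself a change that 7.14 should record.

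Three stronger readings are tempting, and the documents do not support them.

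- A reader might infer that dilution would hide or reverse a true increase. The documents give no urine sodium values, so the direction of the concentration change is unknown. The ovine and first-in-human flow figures come from an animal model and from four patients in a different setting; they show plausibility only.
- A reader might infer that every input is available every 12 hours. Sodium is, but after the first day volume is scheduled every 24 hours, and after retrieval it is generally unavailable.
- A reader might take it as stated that the samples are spot concentrations. That is inferred from the point-in-time schedule and from the concentration units in the albumin-creatinine formula (mg/dL over g/dL).

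**Conclusion.** The point holds as a mismatch between a listed outcome and its analysis. Following the SAP as written reports a different quantity from the one listed, and the departure is not declared. The summary could point the opposite way to excretion: at an assumed 1.5-fold, 2-fold or 10-fold flow, a fall in concentration of up to 33%, 50% or 90% would still go with a rise in excretion. Whether this would happen in these patients cannot be judged from the documents.

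The conclusion rests on one inference, that the recorded urine sodium is a concentration from a sample at a point in time. No primary endpoint is affected. The change is desirable rather than essential.

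**What to change.** Add to the derived parameters in SAP 7.9.2:

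- **Definition.** Sodium excretion rate (mmol/h) = urine sodium (mmol/L) × urine volume recorded over the interval (L) / interval length (h), using actual clock times. State the unit and sample type of urine sodium.
- **Scope.** The pre-implant interval, and on-therapy intervals with a matching recorded volume. Name the pre-implant interval; the one that 7.8.3.1 uses for the baseline hourly rate would keep the two analyses consistent.
- **Pairing.** After day 1, say how 12-hourly sodium values are paired with, or averaged within, each 24-hour volume interval. State that the sample is assumed to represent the interval.
- **Change.** Report change from the pre-implant rate to the last pre-retrieval interval that has both sodium and volume. This matches the end timepoint that 7.14 adopts for urine output. Urine sodium is not scheduled at the cath-lab pre-retrieval assessment, so the last usable sample will be an earlier one.
- **Outputs.** Add the rate to the urine labs table and the urine chemistry listing. Label the 72-hour/discharge and 30-day values as urine sodium concentration, not excretion.

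Fractional excretion of sodium could be an optional supplement. It needs no volume, and the paired serum and urine sodium and creatinine are already scheduled, including at 72 hours/discharge and 30 days. It is not itself a listed outcome.

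If the sponsor prefers not to derive a rate, rename the item as change in urine sodium concentration and record that in 7.14.

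The cost is minor programming and no new data collection. The downside is that the rate is an approximation, because a sample taken within an interval may not represent all the urine in it.
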